7.10 Updates to Secondary Outcome Analytic Methods

Following database lock, it was determined the planned model-based analyses for the secondary outcome measure could not be completed due to limitations in the data, particularly a lack of variability in the UDS data, estimates at the boundary of the parameter space, and small subgroup sample sizes. This led to highly imprecise estimates which were considered unreliable.

7.10.1 Secondary Outcome Analyses

The following changes to the analysis plan for the secondary outcome measure, including the main analysis, demographic subgroup analyses, and supportive analyses, were presented by DSC statisticians to the Lead Node on 02OCT2024. During this presentation, limited summary statistics were presented to the LN to illustrate the issues encountered during analysis. This included three redacted summary tables with masked treatment arm and subgroup names. Note that no results were presented; percentages only (no counts) were used, and no measures of significance were shown. The Lead Investigator and LN statisticians reviewed and made decisions regarding alternative modelling approaches to consider given the lack of variability and parameter space boundary issues. Thus, the additional analytic method decisions were made by parties that had not been privy to any unblinded information regarding the secondary outcome that could possibly impact their determination.

The general approach to dealing with models specified in version 1.0 of the SAP that produced unreliable results is as follows. If the original generalized linear mixed model including fixed effects for treatment, major depressive episode (MDE), week, and site and a random effect for participant converges and produces reliable results, the model will be used and results reported, as pre-specified in the initial version of the SAP. If that model does not converge or produce reliable results (e.g. an OR confidence interval limit over 50), a simplified model will be attempted. The simplified model will include a fixed effect for treatment arm and a random effect for participant. If the simplified model does not converge or produce reliable results, only the summary statistics for percentage negative UDS by primary substance of use, treatment arm, and subgroup (as applicable) will be presented.

If the model does not converge or produce reliable results due only to no variability in a subgroup, results will be presented within the other levels of the subgroup. This may occur if there are no participants in one treatment arm of a subgroup or all participants in that subgroup have no positive UDS results. No p-value will be reported as there is no planned test for significance between treatment arm and subgroup.

Furthermore, demographic and supportive analyses subgroups with three or more levels will be collapsed down to two levels: race (White, Non-White), employment status (Employed, Unemployed), and site (BSW UT Health San Antonio; SC Wake Forest, BSW University of Texas Southwestern, and SC MUSC Department of Psychiatry).

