7.10.2 Missing Data Analysis

The analysis method for imputation will follow that used for the secondary outcome analysis. If the full original model does not produce reliable results, the simplified model with a fixed effect for treatment arm and a random effect for participant will be used. If the simplified model does not converge or produce reliable results, summary statistics will be reported.

Multiple imputation results may not be reported if the planned imputation algorithms fail due to lack of variability in the observed data.

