9.0 SIGNIFICANCE TESTING AND MULTIPLICITY

The secondary (efficacy) outcome will be evaluated using a two-sided test on the significance of the treatment parameter in the proposed model with a Type I error rate of 5%. No attempt will be made to control family-wise Type I error rate when testing for CUD and MUD participants. No other hypothesis testing is planned for the primary or secondary outcomes.

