³ Employed includes working now, temporarily laid off, sick leave, or maternity leave.

⁴ Other includes retired, disabled (permanently or temporarily), keeping house, student, and other. Missing or refused responses are not included in the analysis (N=X).

Table 54: Summary of Secondary Outcome Analysis by Major Depressive Episode

Primary Substance of Use	Major Depressive Episode ¹	Number of Participants Randomized	Treatment Arm		Results ³			
			Sham (N=XX)	rTMS (N=XX)				
			Percentage Negative UDS ²	Percentage Negative UDS ²	Odds Ratio	95% Lower Confidence Limit	95% Upper Confidence Limit	p-value
Cocaine	Present	N	n/N (XX.X%)	n/N (XX.X%)	X.XX	X.XX	X.XX	0.xxx
	Absent							
Methamphetamine	Present							
	Absent							

¹ Major Depressive Episode is assessed for current MDE at baseline.

² Outcome is defined as the percentage calculated by the number of negative UDS divided by the number total UDS performed; it includes the last UDS per study week over the 8-week treatment period in the participant's primary substance of use assessed at randomization. Missing UDS are not imputed.

³ Results are obtained from the generalized linear mixed model. The odds ratios and p-values result from the MDE term.

[figure not shown]
Table 55: Summary of Secondary Outcome Analysis by Site

Primary Substance of Use	Site	Number of Participants Randomized	Treatment Arm		Results ³			
			Sham (N=XX)	rTMS (N=XX)				
			Percentage Negative UDS ²	Percentage Negative UDS ²	Odds Ratio	95% Lower Confidence Limit	95% Upper Confidence Limit	p-value
Cocaine	Site 1	N	n/N (XX.X%)	n/N (XX.X%)	X.XX	X.XX	X.XX	0.xxx
	Site 2							
	Site 3							
	Site 4							
Methamphetamine	Site 1							
	Site 2							
	Site 3							
	Site 4							

¹ Outcome is defined as the percentage calculated by the number of negative UDS divided by the number total UDS performed; it includes the last UDS per study week over the 8-week treatment period in the participant's primary substance of use assessed at randomization. Missing UDS are not imputed.

² Results are obtained from the generalized linear mixed model. The odds ratios and p-values result from the site term.

Figure 6: Forest Plot of Secondary Outcome Results

Example figure provided.

Table 56: Summary of Secondary Outcome Analysis: Participant Effect

Primary Substance of Use	Number of Participants Randomized	Within Participant Correlation Results ¹			
		Estimate	Standard Error	95% Lower Confidence Limit	95% Upper Confidence Limit

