Table 59: Summary of Negative UDS Results in Participants with rTMS Session Threshold Met¹ by Treatment Arm

Primary Substance of Use	Treatment Arm	Number of Participants with Threshold Met	Results ³				
			Percentage Negative UDS ²	Odds Ratio	95% Lower Confidence Limit	95% Upper Confidence Limit	p-value
Cocaine	Sham	N	n/N (XX.X%)	X.XX	X.XX	X.XX	0.xxx
	rTMS						
Methamphetamine	Sham						
	rTMS						
Overall	Sham						
	rTMS						

¹ Participants met the rTMS session threshold if they completed at least 20 rTMS sessions.

² Outcome is defined as the percentage calculated by the number of negative UDS divided by the number total UDS performed; it includes the last UDS per study week over the 8-week treatment period in the participant's primary substance of use assessed at randomization. Missing UDS are not imputed.

³ Results are obtained from the treatment arm term of the generalized linear mixed model.

Table 60: Summary of Secondary Outcome Sensitivity Analysis by Treatment Arm

Method	Results	N	Odds Ratio	95% Lower Confidence Limit	95% Upper Confidence Limit	p-value
Protocol defined secondary outcome	Secondary outcome (missing UDS not imputed)	N	X.XX	X.XX	X.XX	0.xxx
Sensitivity analysis: Time	Study Week defined as strict 7-day window					
	Time defined using Study Day					
Imputation of missing UDS	Missing UDS imputed as negative					
	Missing UDS imputed as positive					
	Missing UDS imputed based on self-reported use (TLFB)					
	Multiple imputation					

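### SAP 7.10.1: if both models fail, a substance group gets percentages only, with no between-arm estimate or interval, and the only numeric guide to model reliability is one-sided (minor)

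*SAP*

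**What the plan says.** SAP 7.5 plans, separately for cocaine (CUD) and methamphetamine (MUD) use disorder, a random-intercept logistic model of weekly UDS. It reports an odds ratio (OR), 95% CI and p-value, and an OR above 1 favours active rTMS. SAP 9.0 adds: "The secondary (efficacy) outcome will be evaluated using a two-sided test on the significance of the treatment parameter in the proposed model".

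SAP 7.10 records that after database lock these models could not be completed as planned, because of little variability in the UDS data, boundary estimates and small subgroups: "This led to highly imprecise estimates which were considered unreliable".

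SAP 7.10.1 then sets three steps.

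- The planned model is used if it converges and is reliable.
- Otherwise: "If that model does not converge or produce reliable results (e.g. an OR confidence interval limit over 50), a simplified model will be attempted". This second model keeps treatment and the participant random effect.
- If that fails too, "only the summary statistics for percentage negative UDS by primary substance of use, treatment arm, and subgroup (as applicable) will be presented".

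SAP 7.10.2 carries the same steps to the missing-data analyses: "If the simplified model does not converge or produce reliable results, summary statistics will be reported". On who decided, 7.10.1 states that "the additional analytic method decisions were made by parties that had not been privy to any unblinded information regarding the secondary outcome". SAP 2.1 gives the purpose of the efficacy outcome as examining the effect size of rTMS against sham for the design of later trials.

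**The concern.** The main issue is the last step. The Table 47 footnote defines the percentage as negative UDS divided by UDS performed, so tests are pooled across participants. A participant with eight screens counts eight times as much as one with a single screen, and the counts alone give no interval that allows for correlation within a participant. A substance group that reaches this step has no reported estimate of the difference between arms and no statement of its uncertainty, which is what a later trial would need from this pilot.

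The second issue is the gate. The word reliable decides at both model steps whether an OR is reported, and its only numeric illustration is a confidence limit over 50. There is no low-side counterpart. Nor is it said which OR is meant, although the supportive analyses under the same rule include ORs for other terms (Table 54 footnote: "The odds ratios and p-values result from the MDE term"). If analysts adopt the example as the cut-off, a favourable treatment OR is abandoned at a precision at which an equally imprecise unfavourable one is kept.

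**Working it through.** **1. Check of the simulation model against the plan's figures.** Inputs from SAP 10.2: 8 UDS per participant, sham probability 0.36, N=80, 1:1 allocation, random-effect SD 1.05 (ICC 0.25) or 1.81 (ICC 0.5), two-sided 0.05. A treatment-only random-intercept logistic fit with a Wald test, 5,000 runs per cell, was set against Protocol Table 8 (repeated in the SAP):

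| ICC | OR 2 | OR 3 | OR 4 | OR 5 |
|---|---|---|---|---|
| 0.5, plan | 35% | 69% | 86% | 94% |
| 0.5, simulated | 34.8% | 67.3% | 84.9% | 93.3% |
| 0.25, plan | 67% | 96% | 100% | 100% |
| 0.25, simulated | 66.5% | 96.4% | 99.6% | 100% |

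All eight agree within 2 points. This supports the simulation model; it says nothing about the fallback itself.

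**2. What can be estimated when both models fail.** Take each participant's percent negative weekly UDS and compare arm means with a Welch 95% CI. Assumptions: n=52 (the CUD count in SAP 11.1.1), sham probability 0.07 at zero random effect (the SAP masks the observed value), 4 sites, MDE in 30%, blocks of 4, ICC 0.25, 0.5 and 0.75, UDS complete or about 25% missing, 1,000 runs. Coverage was 93.7–96.6%, with half-widths of 8 to 20 percentage points. A separate simulation at n=52 and sham probability 0.07 gave coverage of 94–99%. A usable difference and interval therefore remain available.

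**3. Where the example cut-off acts.** The upper limit exceeds 50 when ln OR + 1.96·SE > ln 50, that is, when SE > (3.912 − ln OR)/1.96.

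- OR 3: (3.912 − 1.099)/1.96 = 1.435
- OR 1: 3.912/1.96 = 1.996
- OR 1/3: (3.912 + 1.099)/1.96 = 2.556

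For example, at SE 1.5 an OR of 3 has limits 0.16 to 56.7 and would be dropped, while an OR of 1/3 has limits 0.018 to 6.3 and would be kept. Both intervals have the same limit ratio, exp(2 × 1.96 × 1.5) ≈ 358. These thresholds are algebra and need no assumption about the data.

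**4. How often it acts.** Treatment-only model, 26 per arm, complete UDS, sham probability 0.07, 500 runs per cell; an arm with no negative UDS counts as leaving. Share of fits with upper limit over 50:

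| ICC | true OR 2 / 3 / 4 | true OR 1/2, 1/3, 1/4 |
|---|---|---|
| 0.25 | 0 / 0.4 / 0.2% | 0 / 0.2 / 0.2% |
| 0.5 | 0.4 / 2.2 / 5.6% | 0 / 0 / 0.2% |
| 0.75 (above the plan's range) | 14.8 / 17.4 / 25.6% | 1.6 / 0.4 / 0.4% |

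Over sham probabilities 0.05–0.09 at the plan's ICCs, the range for OR 2–4 is 0–5.6% with complete data. With about 25% of UDS missing (an assumed 6% weekly dropout plus 10% intermittent) it is 0–9.3%, against 0–4.7% for the mirror ORs. In a run of the whole fallback (sham probability 0.07, complete UDS, true OR 3, 250 runs) the last step was reached in 0.4% (ICC 0.25) and 2.0% (ICC 0.5).

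**The case against.** The example is introduced by e.g., so it illustrates reliability and does not define it. The grounds in 7.10 (low variability, boundary estimates, imprecision) are direction-neutral, and a boundary fit with a lower limit of 0.01 falls under them. Under near-separation both directions would leave. This stands: the asymmetry is conditional on using the example as the rule.

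The SAP's data-informed power figures also point to a smaller effect. SAP Table 7 gives 53% (OR 2) and 94% (OR 3) at n=52. A sham probability of 0.07 with almost no between-participant variation (SD 0 to 0.25) gives 50–55% and 92–96%, close to those figures, and there the limit exceeds 50 in only 0–0.8% of fits. This stands too, with the caveat that 7.10 reports highly imprecise fits in the final data, which may differ from the December 2023 freeze.

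Declining inference after two failed models is a defensible, cautious choice in a pilot stated not to be powered for efficacy, and Tables 47 and 48 show percentages by arm, so a crude difference can be subtracted by hand. That is fair about the test. It does not supply an interval that respects within-participant correlation, and step 2 shows that one is available.

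A reader might infer that 7.10 secretly contradicts 7.5 and 9.0. It does not: it is headed as an update, says that it changes the main, subgroup and supportive analyses, and appears in the version log. What is missing is a cross-reference.

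**Conclusion.** The point holds as a minor one. At the last step a substance group is left without a between-arm estimate or interval, which falls short of the effect-size purpose in SAP 2.1 although such an estimate remains computable. The one-sided example is secondary: about 0–6% of complete-data fits at the plan's ICCs, assuming n=52, sham probability 0.05–0.09 and true OR 2–4. The larger rates at ICC 0.75 lie outside the plan's assumptions.

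Three stronger conclusions are tempting and not supported.

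- A reader might infer that the rule favours active rTMS. Where the example acts, it removes favourable estimates, so its one-sidedness cannot create a false claim of benefit.
- A reader might infer that the fallback was chosen with knowledge of the results. The SAP says that the decision-makers saw masked percentages only, and nothing in the documents contradicts this.
- A reader might infer that this trial's efficacy results were distorted. The documents do not show the fits or the sham rate, so this cannot be determined.

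The primary feasibility outcome is a proportion with a Wilson interval and is not touched.

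**What to change.** (a) In 7.10.1, at the last step and in addition to the percentages, report for CUD and MUD separately the between-arm difference in participant-level percent negative weekly UDS with a 95% CI. Label it post hoc and on a different scale from the planned OR. A permutation test within the randomisation strata (site by MDE) is optional.

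(b) In 7.10.1, and by reference 7.10.2, state the reliability criterion for the treatment OR in a direction-neutral form at both model steps. Options are a cap on SE(log OR), a cap on the ratio of the limits, or symmetric limits such as 1/50 to 50. The value should be set by staff without arm-level results, and the report should say which criterion each abandoned model failed. The choice has consequences. A cap of SE 2.0 (limit ratio about 50² = 2500) screens little: OR 3 at SE 1.9 passes with limits of 0.07 to 124. Symmetric limits would remove 0.8–13% of complete-data fits at true OR 1/2 to 1/4 (sham probability 0.07, ICC 0.25–0.5) and restore no favourable fit.

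(c) Editorial follow-ons: refer to 7.10 in 7.5 and 9.0, and add percentage columns to Table 60 ("Summary of Secondary Outcome Sensitivity Analysis by Treatment Arm"). Its shell has columns only for N, OR, limits and p-value, so it cannot hold the summary statistics that 7.10.2 promises.

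The cost is SAP wording, one table shell and one extra descriptive analysis.

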10.3 Randomization

Following determination of full study eligibility via screening, and completion of baseline assessments, participants will be randomly assigned to one of the two conditions (rTMS or sham) for 8 weeks. Random assignment will be on a 1:1 ratio to one of the two conditions. Randomization will be stratified by study site, presence/absence of current major depressive episode, and primary CUD or MUD designation. The randomization procedure will be conducted centrally through the CTN DSC, and randomization assignments will not be conveyed to local research staff or participants. The randomization schedule will be programmed into the rTMS machine so that neither the participant nor the rTMS Operator or research staff knows what condition was assigned. The DSC statistician will generate the randomization schedule using balanced blocks of varying sizes within strata to ensure lack of predictability along with relative equality of assignments across treatment groups. The DSC statistician will review randomization data on a regular basis to ensure that the scheme is being implemented according to plan. A randomization slot, once used, will not be re-allocated, due to the intent-to-treat nature of the study.

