2.2.4 Randomization

Following determination of full study eligibility via screening, participants will be randomly assigned to one of the two conditions (active rTMS or sham) for 8 weeks of treatment. Random assignment will be on a 1:1 ratio to one of the two conditions. Randomization will be stratified based on study site, presence/absence of current major depressive episode (MDE), and whether the participant enters on primary substance of use CUD or MUD. The sample size within each of CUD and MUD is assumed to be 80. The randomization procedure will be conducted centrally through the DSC, and randomization assignments will not be conveyed to research staff (including rTMS Operators) or participants. The unblinded DSC statistician will generate the randomization

schedule using balanced blocks of varying sizes within strata to ensure lack of predictability along with relative equality of assignments across treatment groups. The unblinded DSC statistician will review randomization data on a regular basis to ensure that the scheme is being implemented according to plan. A randomization slot, once used, will not be re-allocated due to the intent-to-treat (ITT) nature of the study. Further details can be found in the Randomization Plan.

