7.5 Analyses of the Secondary Outcome Measures

The secondary (efficacy) outcome will be analyzed in the ITT population (defined in Section 3.1.3) with a generalized linear mixed model approach to adjust for correlation between UDS from the same participants and to provide conditional interpretation of the treatment effect. The model will include fixed effects for treatment, major depressive episode (MDE), week, and site and a random effect for participant. It is important to note that a repeated measure, binary response of negative UDS, for each UDS provided by each participant, will be used as the outcome, as opposed to the total percentage of negative UDS. The model used still allows inference on the overall probability of a negative weekly UDS during the treatment period. Additionally, week will enter the model as a categorical variable to allow greater flexibility on the effect of week. Section 7.9 describes missing data handling procedures for the secondary outcome sensitivity analyses.

The assessment of the significance of the treatment will be done by testing the significance of the treatment parameter at the 0.05 significance level. The treatment effect will be measured by an odds ratio with an associated 95% confidence interval. The corresponding SAS code is provided below:

```
proc glimmix data = data method = quad;
  class site week participant;
  model y(event = '1') = trt mde week site / dist = binary link
    = logit solution;
  random intercept / subject = participant;
run;
```

where:

- data is a dataset with one row per weekly UDS per participant for the specified primary substance of use,
- y is the binary variable with a value of 1 indicating the UDS for that participant was negative and 0 indicating positive UDS result,
- trt is a binary variable with a value of 1 indicating active rTMS and 0 indicating sham rTMS,
- mde is a binary variable with a value of 1 indicating the presence of MDE,
- week is the study week (1 – 8, categorical), and
- site is a categorical variable containing which of the sites each participant was enrolled in.

In the event that the estimate of the variance component related to the within participant correlation (i.e., the ICC for UDS) is so close to 0 that it causes the overall covariance matrix to not be positive definite, the model will be refit without the random effect for the correlation within participant. This is accomplished simply by removing the random effect.

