7.9 Missing Data Analysis

As defined, the primary (feasibility) outcome will have no missing data. Participants that drop out of treatment early will still be evaluated as to whether they attended at least 20 rTMS sessions.

The secondary (efficacy) outcome is expected to have missing data, specifically UDS results. The proposed analysis model takes into account all available data, and missing data are assumed to be missing at random (a weaker assumption than missing completely at random). That is, missingness is allowed to depend on observed covariates. As such, the prespecified analysis method does not need missing data to be imputed or handled in some special way. That being said, alternative methods of handling missing data may be considered as sensitivity analyses.

The first and second methods for missing data analysis will include: 1) imputing all missing secondary outcome measure UDS as negative, and 2) imputing as positive. If there is at least one UDS per study week for a participant, regardless of the timing within the study week or later visits in the study week with missing UDS collection, the outcome is not considered missing. On the other hand, if there is not a single UDS collected within the study week, then the secondary outcome is considered missing.

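### The fallback efficacy model in SAP 7.10.1 drops week, MDE and site in one step; if screens are lost unequally by arm over time, part of any time trend enters the treatment odds ratio.

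*SAP*

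**What the plan says.** SAP 7.5 sets the planned model, fitted separately for the cocaine and methamphetamine groups: "The model will include fixed effects for treatment, major depressive episode (MDE), week, and site and a random effect for participant". On time it adds that "week will enter the model as a categorical variable to allow greater flexibility on the effect of week".

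SAP 7.10 reports that, after database lock, the planned model-based analyses could not be carried out, because the screen results varied too little, some estimates lay on the boundary and some subgroups were small. SAP 7.10.1 then gives the rule: "If that model does not converge or produce reliable results (e.g. an OR confidence interval limit over 50), a simplified model will be attempted". Of that model it says: "The simplified model will include a fixed effect for treatment arm and a random effect for participant". If this also fails, only summary percentages are reported. SAP 7.10.2 carries the same rule, with the same two terms, into the imputation analyses: "If the full original model does not produce reliable results, the simplified model with a fixed effect for treatment arm and a random effect".

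Two other places bear on this. Protocol 10.3 states: "Randomization will be stratified by study site, presence/absence of current major depressive episode, and primary CUD or MUD designation". Within each substance group the strata are therefore site and MDE. SAP 7.9 justifies leaving missing screens unimputed in the main analysis because "missingness is allowed to depend on observed covariates".

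**The concern.** The step-down has one rung. It removes the seven week indicators and the site indicators, which are natural suspects when data are sparse. In the same move it removes a binary stratum and any account of time. Since SAP 7.10 says the planned analyses could not be completed, this model may lie behind the reported odds ratio.

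The time term matters most. SAP 7.4 collects screens at treatment sessions, so a participant who stops attending largely stops contributing. If one arm stops sooner, its observed screens come from earlier weeks. If negative rates are also drifting, a model without week reads the difference in calendar as a difference between arms.

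A second consequence concerns SAP 7.6.3 item 2, which re-runs the analysis with time as continuous Study Day. If that row and the main row both fall back, neither has a time term, they use the same screens, and the two rows are the same analysis.

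**Working it through.** **Inputs from the documents.** Eight weekly binary screens; sham probability of a negative screen 0.36; random-intercept SD 1.81 (ICC 0.5) or 1.05 (ICC 0.25); 80 participants per substance group, 1:1 (Protocol 15.2.2, SAP 10.2); 52 recruited in the cocaine group at the December 2023 freeze (SAP 11.1.1); two-sided 5% test (SAP 9.0).

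**Inputs assumed, because the documents do not give them.** A linear change in log-odds per week of 0, 0.1, 0.2 or 0.4. Over seven weekly steps this is an odds ratio of exp(7 × slope) = 1, 2.0, 4.1 or 16.4. Cumulative dropout by Week 8, active/sham: 30/30, 20/40, 10/50 or 10/80 percent.

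**Method.** Random-intercept logistic model by maximum likelihood (25-point Gauss-Hermite quadrature), Wald test, 1,500 data sets per scenario; Monte Carlo SE about 0.6 points for a rejection rate near 6%.

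**Reproducing the plan's figures first (Protocol Table 8, full model, probability 0.36).**
- N=80, OR 4, ICC 0.5: 87.1% against the stated 86%.
- N=80, OR 2, ICC 0.25: 68.5% against 67%.
- N=80, OR 2, ICC 0.5: 36.6% against 35%.
- N=60, OR 4, ICC 0.5: 76.1% against 75%.

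All are within 2 points.

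**Then with no treatment effect (true OR 1).** N=80, SD 1.81 and probability 0.36 unless stated. OR = exp(mean log-OR).

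| Slope | Dropout % active/sham | Fallback mean log-OR | OR | Fallback rejects | Full model rejects | Fallback + linear week: mean log-OR, rejects |
|---|---|---|---|---|---|---|
| 0 | none | 0.002 | 1.00 | 5.7% | 6.6% | 0.002, 5.7% |
| 0.2 | 30/30 | 0.000 | 1.00 | 5.6% | 6.9% | 0.000, 5.8% |
| 0 | 10/50 | -0.001 | 1.00 | 5.7% | 6.8% | 0.000, 5.9% |
| 0.1 | 20/40 | 0.032 | 1.03 | 5.8% | 6.9% | -0.002, 5.7% |
| 0.2 | 20/40 | 0.067 | 1.07 | 6.0% | 6.7% | 0.001, 5.9% |
| 0.2 | 10/50 | 0.137 | 1.15 | 7.2% | 7.0% | 0.002, 5.4% |
| 0.2, probability 0.03, N=52 | 10/50 | 0.119 | 1.13 | 6.3% | 7.0% | -0.008, 6.5% |
| 0.4 | 10/50 | 0.244 | 1.28 | 9.6% | 6.7% | 0.002, 5.3% |
| 0.4, N=52 | 10/50 | 0.237 | 1.27 | 7.5% | 6.5% | -0.011, 5.4% |
| 0.4, SD 1.05 | 10/50 | 0.209 | 1.23 | 11.7% | 6.0% | 0.002, 4.9% |
| 0.4 | 10/80 | 0.536 | 1.71 | 21.9% | 6.7% | 0.011, 5.9% |

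The mechanism shows in the mean week of the observed screens. At 10/50 it is 4.42 in the active arm and 3.97 in sham; at 30/30 it is 4.23 in both. The share of the Week 1 to Week 8 change that leaks is bias ÷ (7 × slope): 0.067/1.4 = 5%, 0.137/1.4 = 10%, 0.244/2.8 = 9%, 0.536/2.8 = 19%.

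A separate large-sample calculation (slope 0.3, 16 data sets of 3,000 participants per scenario) gave a ratio of simplified to adjusted OR of 0.86 or 1.16 at 50% against 20% dropout, depending on which arm loses more, and 0.91 at 40% against 20%.

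**Strata alone** (MDE log-OR 1, site 0.5 per level, no trend, no dropout): fallback mean log-OR 0.009, rejection 5.3%, so no bias. The spread of the estimates was 0.507 with or without the strata. Under a stronger assumed MDE effect (log-odds 1.5, n=80) the SE was 0.509 without MDE and 0.472 with it: 0.509/0.472 = 1.08.

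**Would an intermediate step fit when the full model fails?** This used n=52, ICC 0.5, 40% dropout in both arms and 150 data sets per setting. Failure meant an upper limit over 50, a coefficient beyond 8 in size, or no usable SE.

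| Negative screens | Full model failed | Treatment + MDE + linear week then fitted | Arm-only then fitted |
|---|---|---|---|
| about 10% | 47 of 150 | 43 of 47 | 44 of 47 |
| about 8% | 68 of 150 | 64 of 68 | 63 of 68 |
| about 5% | 123 of 150 | 108 of 123 | 118 of 123 |

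**The case against.** The strongest reply is that the effect is small against the noise and rests on conditions nobody has shown. A bias of 0.137 is 0.30 of the fallback's own SE (0.137/0.456). In that scenario the fallback rejects 7.2% and the full model 7.0%, so moderate settings add almost no false positives. This is a secondary outcome in a pilot that the SAP says is not powered for efficacy. A steep trend also sits awkwardly with data described as lacking variability. All of this stands, and it limits the point to one worth correcting.

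There are partial safeguards. SAP Tables 46 and 48 show availability and negative screens by week and arm, so a reader could see both conditions. The rows that impute every missing screen as negative or as positive fill all eight weeks in both arms, so week is balanced there. These reveal the problem; they do not correct the main odds ratio.

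Four stronger readings are tempting, and the documents do not support them:
- That any time trend becomes a treatment effect. Only part leaks, and a trend with equal dropout, or unequal dropout with no trend, gave an OR of 1.00.
- That omitting MDE and site biases the estimate. It does not.
- That the fallback loses the missing-at-random argument of SAP 7.9 altogether. It keeps arm, and the likelihood uses each participant's observed screens. What is lost is week in the mean model.
- That rows of Table 60 will come from different models. SAP 7.10.2 opens by tying the imputation analyses to the method of the main analysis, then restates the trigger. Whether the model is chosen once or row by row is ambiguous.

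**Conclusion.** The point holds in a limited form. The fallback has no step that keeps time or a stratum, and it can carry part of a time trend into the treatment odds ratio when two things occur together: unequal loss of screens by arm over time, and a changing negative rate. With a true odds ratio of 1, the size is about 1.03 to 1.15 for moderate assumptions and about 1.28 with 9.6% rejection for a steep trend with 10% against 50% dropout. The direction depends on which arm loses more screens and which way the trend runs. Only the most extreme setting tried (10% against 80%) reached 1.71.

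Dropping MDE and site is a departure from the stratified design with a possible loss of precision: none in one scenario, about 8% on the SE under a strong MDE effect. Separately, the Study Day row becomes uninformative once both it and the main row fall back.

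These figures rest on assumed trends and dropout. The linear week term removed the bias for trends that were generated as linear; with a curved trend some bias could remain.

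**What to change.** In SAP 7.10.1, replace the single jump by a stated sequence:

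1. the full model;
2. treatment, MDE and linear week, with a random participant intercept;
3. treatment and linear week, with a random participant intercept;
4. the present arm-only model;
5. summary statistics.

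In SAP 7.10.2, state that the model chosen in the main analysis for each substance group is used for every row of Table 60 and for all 50 imputed data sets, apart from the time term that a row is designed to vary. The Study Day row would then carry Study Day in place of week.

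Because the database is locked, label the added steps as post-lock. If fallback results already exist, report the intermediate model beside them as a sensitivity analysis and do not substitute it.

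The cost is a paragraph of SAP text, a few more fits, one or two extra parameters, and one more modelling decision taken after lock. Step 2 still drops site and step 3 drops MDE, so the design is only partly respected if the data are too sparse for more.
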